#### Osteoarticular

For ease of data analysis, the statistician will convert the scores from the original database to a “long” format, with the following columns:

- RDMNUM
- Visit (1/2/3/4)
- is\_crb
- is\_PP
- WABAQ
- dWABAQ \*
- NIHSST
- dNIHSST \*
- BIT \*
- MRS \*

Columns starting with a *d* represent changes in scores at visits 2/3/4 compared to visit 1 (baseline). Columns marked with \* have values only for visit 2/3/4.

The column *is\_crb* will have a true/false value, depending on whether the patient was assigned to the treatment or placebo group. The column *is\_PP* will have a true/false value, depending on whether the specified data point will be analyzed as part of the *Per Protocol* analysis set. This is a mechanism through which the statistician or any other authorized person can exclude specific patients from each analysis set, depending on criteria such as protocol violations or patient withdrawal, and then prepare the subset for the statistical analysis routine. Assignment of each patient to the correct analysis sets is described later in this document.

AE-related data will be coded and analyzed in a separate database, with the following structure:

- RDMNUM
- SAE (is the AE a SAE?)

- AE\_total (the number of total AEs accused by the patient)
- SAE\_total (the number of total SAEs accused by the patient)
- Number of AEs accused by the patient, by category
  - AE\_cardiovascular
  - AE\_renal
  - ...

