## Randomisation

Randomisation was discussed at length in the CSP. Briefly, patients meeting inclusion and exclusion criteria will obtain a random number corresponding to the random list generated in advance by a biometrician selected by the Coordinator. Three opaque randomization envelopes will be distributed: to the nurse in charge of preparing the infusion solution, to the study center in case of suspicion of harm to the patient, as well as to the study coordinator.

The study and database will be unblinded after closure of the database and determination of the analysis populations.

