### Efficacy analysis in Per Protocol population

The Per Protocol population (PP) includes all trial participants who have adhered to the study protocol, received the medication corresponding to the group they were assigned to after randomization, had at most minimal protocol deviations, and no missing values for total scores of Western Aphasia Battery and NIHSS at visits 2, 3 or 4, or missing values for modified Rankin Scale and Barthel Index at visits 3 or 4. This analysis set is used to assess the efficacy of the treatment in ideal conditions. From a missing data handling point of view, the PP population is subject to listwise deletion, meaning that a patient missing one data point is not taken into consideration in any analysis.

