### Efficacy analysis in Intention To Treat population

The Intention To Treat (ITT) population includes all trial participants who were registered in the trial and were randomized, irrespective of their subsequent adherence to the protocol or premature discontinuation. As such, compared to PP, ITT contains all the PP subjects, as well as subjects with major protocol deviations. This analysis set is used to assess the efficacy of the studied treatment, taking into consideration patients not adhering to the protocol (non-compliance,

dropouts, SAEs, unforeseen events), thus better representing the expected results of the treatment in clinical practice. From a missing data handling point of view, the ITT population is subject to pairwise deletion, meaning that a patient missing one data point is still taken into consideration in any analysis that does not require the missing data point.

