## Safety analysis in safety population

The Safety Population (SP) includes all trial participants who were registered in the trial and received at least one dose of treatment, irrespective of their subsequent adherence to the protocol or premature discontinuation. Unlike ITT, SP analysis focuses on AEs and SAEs caused by the treatment, thus evaluating the safety-related parameters of the products. Patients are included in this population irrespective of missing data or premature discontinuation.

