# AE information table -----
db_adver2<-db_assign
for(i in 1:nrow(db_adver2)){
  rdmnum<-db_adver2$RDMNUM[i]
  db_adver2[i,"AE_total"]<-sum(db_advers$RDMNUM==rdmnum)
```

```
db_adver2[i,"SAE_total"]<-sum(db_advers$RDMNUM==rdmnum&db_advers$SAE=="yes")
for(j in
c("neurological","psychiatric","cardiovascular","renal","hematological","gastrointestinal","metabol
ic","respiratory","immune.related.AE","ENT","ophthalmic","osteoarticular"))
  db_adver2[i,paste0("AE_",j)]<-
sum(db_advers$RDMNUM==rdmnum&db_advers[,paste0("is_",j)]==1)
}
tbl_out<-data.frame(
  AE_category=as.character(),
  sub=as.character(),
  Crb=as.character(),
  Plc=as.character(),
  pval=as.character(),
  test=as.character()
)
db_aelong<-data.frame(
  AE_category=as.character(),
  is_crb=as.logical(),
  no_patients=as.numeric(),
  no_aes=as.numeric(),
  percent_patients=as.numeric()
)
for(i in 7:20){
  rws<-nrow(tbl_out)
  tbl_out[rws+1,1]<-db_names[i,"short"]
  tbl_out[rws+1:5,2]<-c("Patients with AEs in group","Total number of AEs in group","Mean
number of AEs per patient","Median (Q1-Q3) number of AEs per patient","Max number of AEs
per patient")
  xc<-db_adver2[db_adver2$is_crb,db_names[i,"short"]]
  xp<-db_adver2[!db_adver2$is_crb,db_names[i,"short"]]
  tbl_out[rws+1,3]<-paste0(sum(xc!=0)," (",round(sum(xc!=0)/length(xc)*100,3),"%)")
  tbl_out[rws+1,4]<-paste0(sum(xp!=0)," (",round(sum(xp!=0)/length(xp)*100,3),"%)")
  x<-contingency.table.test(table(db_adver2$is_crb,db_adver2[,db_names[i,"short"]]!=0))
  tbl_out[rws+1,5]<-beautiful.p.value(x[["p_chosen"]])
  tbl_out[rws+1,6]<-x[["shorthand"]]
  tbl_out[rws+2,3]<-sum(xc)
  tbl_out[rws+2,4]<-sum(xp)
  tbl_out[rws+3,3]<-descr.numeric.meansd(xc)
  tbl_out[rws+3,4]<-descr.numeric.meansd(xp)
  tbl_out[rws+4,3]<-descr.numeric.median(xc)
  tbl_out[rws+4,4]<-descr.numeric.median(xp)
  tbl_out[rws+5,3]<-max(xc)
  tbl_out[rws+5,4]<-max(xp)
  x<-test.numeric.unpaired(xc,xp)
```

```

tbl_out[rws+3,5]<-beautiful.p.value(x$p.value)
tbl_out[rws+3,6]<-x$final.test
for(j in 1:max(xc, xp)){
  tbl_out[rws+5+j,2]<-paste0("Patient with ",j," AEs")
  tbl_out[rws+5+j,3]<-paste0(sum(xc==j)," (",round(sum(xc==j)/length(xc)*100,3),"%)")
  tbl_out[rws+5+j,4]<-paste0(sum(xp==j)," (",round(sum(xp==j)/length(xp)*100,3),"%)")
}
rws<-(i-7)*2
db_aelong[rws+1:2,1]<-db_names[i,"short"]
db_aelong[rws+1:2,2]<-c(T,F)
db_aelong[rws+1,3]<-sum(xc!=0)
db_aelong[rws+2,3]<-sum(xp!=0)
db_aelong[rws+1,4]<-sum(xc)
db_aelong[rws+2,4]<-sum(xp)

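### Safety tables, tests and graphs group patients by arm assigned, although the Safety Population is defined by dosing and is meant to evaluate the products

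*SAP*

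**What the plan says.** Under Coding systems utilized, the SAP defines `is_crb` as a true/false value "depending on whether the patient was assigned to the treatment or placebo group". In the R supplement, the data-loading block reads an assignment file with three columns (`RDMNUM`, `is_crb`, `is_pp`), and a code comment describes its content as group assignment data. The AE information table block then begins with "db_adver2<-db_assign" and separates the arms by `is_crb` throughout.

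The section on the safety population sets membership by exposure: "The Safety Population (SP) includes all trial participants who were registered in the trial and received at least one dose of treatment". It contrasts this set with ITT and says that the analysis concerns events caused by the treatment, "thus evaluating the safety-related parameters of the products". It does not say in which arm a patient is to be analysed. The Exploratory statistics section compares AE incidence between groups, also without saying whether the groups are as assigned or as treated.

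The Per Protocol definition requires that a patient "received the medication corresponding to the group they were assigned to after randomization". The ITT section states that "ITT contains all the PP subjects, as well as subjects with major protocol deviations".

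**The concern.** Grouping by assignment suits ITT. A safety analysis that sets out to describe what the products do should attribute events to the product a patient was exposed to. The SAP states the second aim and codes the first. Because receipt of the assigned product is a Per Protocol criterion, a mismatch between assigned and given product is possible within the plan's own terms. Such a patient leaves the Per Protocol set but stays, without comment, in the assigned column of every safety table.

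The stake is misattribution in a small trial. With 60 patients per arm and few serious events, one patient in the wrong column can alter how a comparison reads. If the question arises only once allocation is known, the choice of column would be made with the results in view.

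**Working it through.** **Trace of the arm variable**

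| Step | Place in the SAP | What it does |
|---|---|---|
| Definition | Coding systems utilized | `is_crb` is the arm assigned |
| Source | R code, loading block | file with `RDMNUM`, `is_crb`, `is_pp`; no column for product received and no safety-set flag |
| AE data frame | R code, AE information table | a copy of that file |
| Counts, percentages, tests | same block | vectors `xc` and `xp` are selected by `is_crb`; the contingency table is also built on it |
| Graphs | same block, to the end | fill and legend N come from `is_crb` |

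No step between loading and output moves a patient to the arm of the product received. Set beside the safety population section, the code answers a question about allocation while the text announces one about products.

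**Scale**

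The SAP states no figure on this point, so there is none to reproduce. The following is an illustration only. The arm size of 60 is from the sample size section; the event counts are assumptions.

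Let a and b be the numbers of patients with an event as assigned to Cerebrolysin and placebo. Suppose one placebo-assigned patient received Cerebrolysin.

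- If that patient had an event, the by-product table is (a+1)/61 v (b−1)/59.
- If that patient had no event, it is a/61 v b/59.

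The SAP's code uses Fisher's exact test when any expected count is below 5. For 7 events in total, the smallest expected count is 7×60/120 = 3.5 as assigned and 7×59/120 = 3.4 as received, so Fisher applies in every row below.

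| As assigned | Misallocated patient | By product received |
|---|---|---|
| 6/60 v 1/60: 10.0% − 1.7% = 8.3 points, p=0.114 | had the event | 7/61 v 0/59: 11.5% − 0% = 11.5 points, p=0.013 |
| 6/60 v 1/60: 8.3 points, p=0.114 | had no event | 6/61 v 1/59: 9.8% − 1.7% = 8.1 points, p=0.114 |
| 5/60 v 2/60: 8.3% − 3.3% = 5.0 points, p=0.44 | had the event | 6/61 v 1/59: 9.8% − 1.7% = 8.1 points, p=0.11 |

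One misallocated patient with an event shifts the risk difference by about 3 points (11.5 − 8.3 = 3.2; 8.1 − 5.0 = 3.1). Without an event the shift is about 0.2 points. The first row crosses 0.05 only because the one misallocated patient is also taken to be the only placebo-arm case.

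**The case against.** The strongest reply is that the SAP nowhere describes or expects a patient infused with the wrong product. The Per Protocol wording does not prove that it does: a randomised patient who was never infused also fails that criterion. A reader might infer that the plan anticipates cross-infusion, but the text supports only that a mismatch is possible. If none happens, the assigned and received tables are identical. This stands, and it makes the effect conditional.

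A reader might also infer that the Per Protocol set cannot be built blind, because no analysis variable shows whether the given product matched the assigned one while the Randomisation section says "The study and database will be unblinded after closure of the database and determination of the analysis populations". The documents do not support this. Under Coding systems utilized, `is_PP` may be set by the statistician or another authorised person for protocol violations, and the code loads that flag ready-made. Someone with access to the preparation information can apply the criterion without passing the arm to the statistician.

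Nor can one say that the product given is unrecorded. The SAP lists only variables of interest for the analysis, so what is shown is its absence from the analysis code and its listed variables.

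Finally, the trial is exploratory and no confirmatory analysis is planned, so no formal decision rests on a safety p-value crossing 0.05. That lowers the weight of the p-values above. It does not remove the mismatch between the stated safety aim and the coded grouping.

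**Conclusion.** The point holds in a limited form. As coded, every safety comparison is by arm assigned, while the Safety Population is defined by dosing and is meant to characterise the products. Any patient given the other product would be counted, in numerator and denominator, under a product not received.

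The size depends on whether this happens at all, for which the SAP gives no rate. With 60 per arm, one such patient with an event moves the risk difference by about 3 percentage points. It can carry a sparse comparison across 0.05 in an unfavourable configuration (0.114 to 0.013), but need not (0.44 to 0.11, or unchanged at 0.114 when the patient had no event). These figures rest on assumed event counts. The point should be settled before unblinding because the change is small and the choice should not be made with results in view.

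**What to change.** - In the safety population section, state that the Safety Population is analysed by the product actually received.
- Add a treatment-received variable to the adverse event data and use it in place of `is_crb` in the AE information table code and the graphs that follow.
- Before unblinding, fix a rule for classifying patients who received both products. Treatment is three cycles of 2 × 5 days, so 3 × 10 = 30 infusions, and an error could affect only some of them; a single received-product value cannot classify such a patient without a rule.
- Footnote every patient whose assigned and received products differ.
- Keep `is_crb` for ITT.

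The cost is one variable, a changed column name in the AE code and a few sentences of text. The downside is that discordant patients leave their randomised group, in the safety tables only. The change assumes that the product given can be obtained from trial records, which the SAP does not describe.

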## Study objectives

### Primary objectives

The primary objective of the ESCAS study is to assess the efficacy of Cerebrolysin and speech therapy versus placebo (saline solution) and speech therapy at 30, 60, and 90 days after baseline. Efficacy will be evaluated using the Western Aphasia Battery (Romanian translated version) scores at each time point. The primary outcome measure is the change in Western Aphasia Battery score from baseline to each follow-up time point (30, 60, and 90 days).

### Secondary objectives

The secondary objectives of the ESCAS study include the following:

- To assess the efficacy of Cerebrolysin and speech therapy versus placebo (saline solution) and speech therapy at 30, 60, and 90 days after baseline using measures of motor, neurological, and global functional outcome. These outcomes will be evaluated using the National Institutes of Health Stroke Scale (NIHSS), Barthel Index (BI), and modified Rankin Scale (mRS) scores at each time point.
- To evaluate the safety of Cerebrolysin and speech therapy versus placebo (saline solution) and speech therapy at 30, 60, and 90 days after baseline. Safety will be assessed by comparing the incidence of adverse events (AEs) and severe adverse events (SAEs) between the two treatment groups.
  - Additionally, we will measure specifically neurological, psychiatric, cardiovascular, renal, hematological, gastrointestinal, metabolic, respiratory, immune-related, ENT, ophthalmic and osteoarticular related adverse events.

The secondary outcome measures include changes in NIHSS, BI, and mRS scores from baseline to each follow-up time point (30, 60, and 90 days), as well as the incidence of AEs and SAEs.

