### Secondary objectives

The secondary objectives of the ESCAS study include the following:

- To assess the efficacy of Cerebrolysin and speech therapy versus placebo (saline solution) and speech therapy at 30, 60, and 90 days after baseline using measures of motor, neurological, and global functional outcome. These outcomes will be evaluated using the National Institutes of Health Stroke Scale (NIHSS), Barthel Index (BI), and modified Rankin Scale (mRS) scores at each time point.

- To evaluate the safety of Cerebrolysin and speech therapy versus placebo (saline solution) and speech therapy at 30, 60, and 90 days after baseline. Safety will be assessed by comparing the incidence of adverse events (AEs) and severe adverse events (SAEs) between the two treatment groups.
  - Additionally, we will measure specifically cardiovascular (such as, but not limited to stroke, myocardial infarction, atherosclerosis, vascular stenosis, as well as their recurrence), hematological (including anemia and vitamin B9 or B12 deficiency), renal system (including hyperuremia, hyperuricemia and urinary tract infections) and metabolic (including dyslipidemia, diabetes mellitus and atherosclerosis) related adverse events.

The secondary outcome measures include changes in NIHSS, BI, and mRS scores from baseline to each follow-up time point (30, 60, and 90 days), as well as the incidence of AEs and SAEs.

By addressing both the primary and secondary objectives, the ESCAS study will provide a comprehensive evaluation of the efficacy and safety of Cerebrolysin in the treatment of aphasia after acute ischemic stroke, in comparison with a placebo control group.

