## Coding systems utilized

The original database uses the following variables which are of interest for the data analysis. In the following list, unless otherwise noted, x represents the moment of measurement (1=baseline, 4=last visit at 90 days after treatment). Note that for Barthel Index and modified Rankin Scale, only scores at visits 2, 3, and 4 (30, 60 and 90 days after baseline, respectively) are available, with no value at baseline.

- RDMNUM = randomization number (unique to each participant)
- 
- Western Aphasia Battery
  - WABAQ\_x = Aphasia Quotient (0-100%)
- NIH Stroke Scale (Score)
  - NIHSST\_x = total score (0-42)
- Barthel Index
  - BIT\_x = total score (0-100)
- Modified Rankin Scale

- MRS\_x = total score (0-6 where 0=no symptom and 6=dead)

AEs and SAEs were stored in a separate database, from which we will retrieve the following information:

- Randomization number
- Whether the AE represents a SAE or not
- Based on the nature of the AE, some will be further classified by a clinician as being of the following nature:
  - Neurological
  - Psychiatric
  - Cardiovascular
  - Renal
  - Hematological
  - Gastrointestinal
  - Metabolic
  - Respiratory
  - Immune-related
  - ENT
  - Ophthalmic

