## Study schedule

### Visit schedule

- Visit 1 - Day 0 - Baseline, 3-5 days post-stroke
  - Demographics
  - Medical history
  - Western Aphasia Battery
  - NIHSS
- Visit 2 - Day 30  $\pm$  3
  - Western Aphasia Battery
  - NIHSS
  - Barthel Index
  - modified Rankin Scale
  - Adverse Events (AE)
  - Severe Adverse Events (SAE)
- Visit 3 - Day 60  $\pm$  3
  - Western Aphasia Battery
  - NIHSS
  - Barthel Index
  - modified Rankin Scale
  - Adverse Events (AE)
  - Severe Adverse Events (SAE)
- Visit 4 - Day 90  $\pm$  3
  - Western Aphasia Battery

- NIHSS
- Barthel Index
- modified Rankin Scale
- Adverse Events (AE)
- Severe Adverse Events (SAE)

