### Efficacy

- Comparison of the National Institutes of Health Stroke Scale (NIHSS) scores between the Cerebrolysin and placebo groups at each time point (30, 60, and 90 days after study inclusion) compared to baseline. The NIHSS is a widely used tool for assessing stroke severity and neurological deficits. Paired-measurement statistical tests will be used to analyze the NIHSS scores for each time point compared to baseline, in each group. Unpaired-measurement statistical tests will be used to determine the differences between efficacy of the treatment between groups, at each time point.
- Comparison of the modified Rankin Scale (mRS) scores between the Cerebrolysin and placebo groups at each follow-up time point (30, 60, and 90 days after study inclusion), as well as comparisons between the scores at 3rd and 4th visits compared to 2nd visit. The mRS is a commonly used measure of global disability and functional outcome in stroke patients.
- Comparison of the Barthel Index (BI) scores between the Cerebrolysin and placebo groups at each follow-up time point (30, 60, and 90 days after study inclusion), as well as comparisons between the scores at 3rd and 4th visits compared to 2nd visit. The BI is a measure of functional independence in activities of daily living.

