## Comparability between study groups

Compatibility between groups will be tested for the following variables: age (at stroke onset), gender, education level, writing hand, alcohol and other substance abuse, WAB scores (and their specific subscales) and NIHSS scores.

- Dichotomous variables will be tested using Chi test or, where its assumptions are not met due to small group size, Fisher's exact test.
- Qualitative ordinal variables, such as education level or alcohol/substance abuse, will be tested using Wilcoxon rank-sum tests.
- For quantitative variables, initially, normality distribution will be assessed for each group individually using the Shapiro-Wilk test. If the values for at least one group are not normally distributed, Wilcoxon rank-sum tests will be used. If values from both groups are normally distributed, equality of variances will be assessed using Bartlett test and then a Student T test for unpaired samples and equal or unequal variances will be used.

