## Exploratory statistics

For WAB scores (and their specific subscales) as well as for NIHSS scores, we will calculate the differences between the scores at visits 2/3/4, and their corresponding baseline scores. These differences will be denoted with a lowercase letter "d." Throughout this section, we will refer to these values as *differentials*.

We will assess the normality of the differentials distributions for each group and visit using the Shapiro-Wilk test.

- If the distributions of the differentials show no statistically significant differences compared to the normal distribution, across all groups and visits, then those differentials will be tested against null hypotheses of  $\mu=0$  using one sample Student T test. This would be the equivalent of testing the values of the scores for each group, at visit 2/3/4, against the baseline measurements of each respective group using paired-sample Student T test. Moreover, for each visit, we will compare the differentials between groups using Student T test for unpaired samples and equal or unequal variances, depending on the result of a Bartlett test for variance equality between groups.
- In cases where significant differences exist in the distribution of the differential values for certain groups and visits, compared to the normal distribution, we will test all differentials against the null hypothesis of location=0 using a one-sample Wilcoxon signed-rank test. This approach is equivalent to comparing the values of the scores for each group at visits 2, 3, and 4 against their corresponding baseline measurements using a Wilcoxon signed-rank test. Moreover, for each visit, we will compare the differentials between groups using a Wilcoxon rank-sum test.

For BI and mRS scores, differences from visit 2 to visit 3 and 4 respectively will be assessed in the same way, with paired-sample tests, and differences between groups will be assessed using unpaired-samples tests. .

The number of patients with at least an active AE, SAE and specific AE class, will be reported. Incidence of AEs, SAEs and AE specific classes will be compared between groups using

Chi test or where its assumptions are violated, Fisher's exact test. Moreover, the number of AEs and SAEs for each patient will be compared between groups using Wilcoxon rank-sum tests.

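### Change from baseline in Barthel Index and mRS is listed as a secondary outcome, but neither scale is measured at baseline; the analysis that replaces it at Days 60 and 90 compares arms only on differences from Day 30

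*SAP*

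**What the plan says.** The SAP describes the BI and mRS outcomes in three ways.

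- **Objectives.** The same sentence closes Secondary objectives under both Objective and Study objectives: "The secondary outcome measures include changes in NIHSS, BI, and mRS scores from baseline to each follow-up time point (30, 60, and 90 days".
- **Endpoints.** Secondary endpoints, Efficacy, treats NIHSS differently from the other two scales. NIHSS is compared with baseline. BI and mRS are compared between arms at each follow-up, "as well as comparisons between the scores at 3rd and 4th visits compared to 2nd visit".
- **Analysis.** Exploratory statistics plans: "For BI and mRS scores, differences from visit 2 to visit 3 and 4 respectively will be assessed in the same way". Planned tables lists, for both scales, differentials of Visits 3 and 4 against Visit 2 and a comparison of those differentials between groups.

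On what data exist, the SAP is consistent. Coding systems utilized says that for BI and mRS "only scores at visits 2, 3, and 4 (30, 60 and 90 days after baseline, respectively) are available, with no value at baseline". In the column list for the long-format database, the BI and mRS columns are among those that "have values only for visit 2/3/4", and no change column is defined for either. The first entry of the Visit schedule, "Visit 1 - Day 0 - Baseline, 3-5 days post-stroke", has WAB and NIHSS as its only scales; BI and mRS first appear at Visit 2.

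**The concern.** An outcome defined as change from baseline needs a baseline value, and for two of the three scales none is collected. Someone writing the report from the objectives would find nothing to put under the stated outcome. The nearest quantity in the output is the difference from Visit 2, and it could easily be reported as if it were change from baseline.

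Two things are at stake. First, three descriptions of the same outcome stand side by side, so the choice among them may be made after the data are seen, which the SAP's own statement of purpose is meant to prevent. Second, the descriptions are different quantities. A difference from Visit 2 removes whatever the treatment had already achieved by Day 30.

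Starting function is also unmeasured. The check under Comparability between study groups covers "WAB scores (and their specific subscales) and NIHSS scores" together with demographics, but no functional scale. That is no error in that section, which can only use what Visit 1 collects. It does mean that a chance imbalance in function at entry cannot be seen directly.

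**Working it through.** **Step 1: count the stated outcomes.** The objectives name 3 scales (NIHSS, BI, mRS) and 3 time points (Days 30, 60, 90).

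- Stated change outcomes: 3 × 3 = 9.
- With a Visit 1 value (NIHSS): 1 × 3 = 3.
- Without a Visit 1 value (BI, mRS): 2 × 3 = 6.

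The six are undefined for all 60 + 60 = 120 planned patients. The R code agrees: baseline differentials are built for the WAB quotient and NIHSS only.

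**Step 2: trace what is tested between arms for BI and mRS.** In the R function `table_them_all`, run for these scales with `already_diff = F`:

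| Visit | Contents of `vc` and `vp` at the between-arm test | Quantity compared |
|---|---|---|
| 2 | scores | score at Day 30 |
| 3 | overwritten by Visit 3 minus Visit 2 | change since Day 30 |
| 4 | overwritten by Visit 4 minus Visit 2 | change since Day 30 |

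The group means and medians in the same output are computed before the overwriting. At Visits 3 and 4 the table therefore shows descriptive statistics of scores next to a p-value for differences. As coded, the between-arm comparison of scores that the endpoint section promises is made at Visit 2 only.

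**Step 3: is Visit 2 a baseline?** Visit 2 is Day 30 ± 3, that is Days 27 to 33. Treatment Cycle 1 occupies study days 1 to 14. Visit 2 therefore falls 27 − 14 = 13 to 33 − 14 = 19 days after that cycle ends. Cycle 2 starts on day 29, so at the nominal Day 30 it has already begun. Visit 2 is a post-treatment measurement.

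**Step 4: compare the three quantities.** Let Δₖ be the between-arm difference in mean score at visit k. Randomisation makes Δ₁ zero in expectation.

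- Change from baseline (objectives): Δₖ − Δ₁, which equals Δₖ in expectation. It cannot be computed here.
- Follow-up score (endpoint section): Δₖ. Computable at Visits 2, 3 and 4.
- Difference from Visit 2 (tables and code): Δₖ − Δ₂. Computable at Visits 3 and 4.

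The follow-up score thus targets the same between-arm contrast as the stated outcome. The Visit 2 difference does not. If a benefit were complete by Day 30 and fully kept, Δ₄ = Δ₂ and the tested quantity at Visit 4 would be zero despite a lasting effect. This algebra concerns means; a rank-sum test does not follow it exactly, but the Day 30 effect is still taken out of each patient's value.

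**The case against.** The best defence is that this is leftover wording in a summary sentence. The objective itself is to compare arms on scores at each time point, which needs no baseline value. The endpoint section already separates BI and mRS from NIHSS. No table, column or line of code attempts a BI or mRS change from baseline, and Planned tables labels its differentials correctly as being against Visit 2. The trial is exploratory, with no confirmatory analysis planned, and a requirement for ordinal or adjusted models would go beyond correcting an inconsistency.

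Much of this stands. A reader might infer that the functional objective cannot be answered by this design. The documents do not support that: randomised arms can be compared on follow-up scores, and the endpoint section plans to do so. Nor do they support the inference that the missing baseline makes such a comparison invalid. Adjustment for NIHSS would improve precision and protect against chance imbalance; it is not a condition for validity, and the choice of model is open.

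What does not stand is that a change of wording in the objectives settles the matter. The endpoint section promises between-arm comparison of scores at every follow-up, while Planned tables and the code deliver differences from Visit 2 at Days 60 and 90. Rewording the objectives to match the endpoint section would leave that second mismatch in place.

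**Conclusion.** The contradiction is real, but limited in scope. Six of the nine secondary change outcomes named in the objectives cannot be computed; the three for NIHSS can. The functional objective in its broader form remains answerable through follow-up scores compared between arms. As tabled and coded, however, the between-arm tests at Days 60 and 90 address change since a visit that follows Cycle 1. That is neither the outcome in the objectives nor the score comparison in the endpoint section.

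These are secondary outcomes in an exploratory trial, so the point should be corrected but does not touch the primary analysis. The count rests only on the SAP's own statements about which scales are collected when. The argument that follow-up scores can stand in for change from baseline between arms rests on randomisation, and on analysing the patients as randomised.

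**What to change.** 1. In both Secondary objectives sections, keep change from baseline for NIHSS only. Define the BI and mRS outcomes as scores at Days 30, 60 and 90 compared between arms, as the endpoint section does.
2. Align Exploratory statistics, Planned tables and `table_them_all` so that the scores themselves are tested between arms at Visits 3 and 4 as well as Visit 2. In the code, hold the Visit 2 differences in separate variables instead of overwriting the scores.
3. If the Visit 2 differences are kept, label them as change since Day 30 throughout, never as change from baseline.
4. Add a between-arm analysis adjusted for baseline NIHSS, which Visit 1 already collects: for example a proportional-odds model for mRS and a rank-based or linear model for BI. Describe it in Statistical analysis as an addition to the unadjusted tests, so that no new contradiction arises.
5. State that no claim of improvement in BI or mRS since baseline will be made.

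The cost is wording in several sections, a small change to one function, one further analysis per scale and possibly an additional R library, which Software utilized allows if its use is explained in the report. No new data are needed. The trial gives up a change-from-baseline claim that its data could not support.
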